10.9 ECHO or MUGA scan

All patients will have an echocardiogram (ECHO) or multiple gated acquisition (MUGA) scan at screening and when it is indicated clinically during the study. A summary table of LVEF will be produced to display baseline result. This information will also be listed along with any optional post-baseline records and includes the method (ECHO, MUGA scan), the LVEF (%), the result (normal, clinically insignificant abnormality, clinically significant abnormality) and the abnormality descriptions.

10.10 Gallbladder assessment

The gallbladder evaluation, either magnetic resonance imaging (MRI) or a computer tomography (CT) scan, will be performed together with the radiological tumor assessment at baseline for all patients, on treatment only for patients treated with pasireotide LAR.

If the patient discontinues treatment, an end of core study visit MRI/CT scan has to be performed only if the end of core study visit occurred 3 months or more after the previous MRI/CT scan.

A table will be presented showing the frequencies at baseline of image performed? (yes, no), were any gallstones detected? (yes, no), was any sludge detected? (yes, no), is there any dilatation of the intra- or extrahepatic ductal system (yes, no) and if yes was it the intrahepatic ductal system or the extrahepatic ductal system, gallbladder imaging technique (CT scan, MRI) and was there any gallbladder thickening (yes, no). Percentages will be calculated based on the number of patients with available data for each of these questions.

A shift table will also be produced for gallstones detection, sludge detection, dilatation and thickening comparing the baseline result with the most extreme post-baseline result (defined as 'yes' if it occurs post-baseline). This will only include the treatments of Pasireotide LAR and both Pasireotide LAR and Everolimus since this data is not collected for patients in the Everolimus group.

A listing will be presented showing the visit, image performed? (yes, no), date, were any gallstones detected? (yes, no) and if yes, the location, was any sludge detected? (yes, no) and if yes, the location, is there any dilatation of the intra- or extrahepatic ductal system (yes, no) and if yes was it the intrahepatic ductal system or the extrahepatic ductal system, gallbladder imaging technique (CT scan, MRI) and was there any gallbladder thickening (yes, no).

10.11 Pulmonary function test

At baseline, prior to administration of study drug, pulmonary function tests (PFT) can be performed, if clinically indicated. During study treatment, all PFTs including spirometry, diffusion capacity for carbon monoxide (DLCO) and room air oxygen saturation at rest must be performed if the patient develops non-infectious pneumonitis. A listing split by treatment will be provided showing the spirometry date, total lung capacity, forced vital capacity (FVC), forced expiratory volume in one second (FEV1), functional residual capacity, residual capacity, was DLCO done? (yes, no) and if yes, the date and capacity, pulse oximetry done? (yes, no) and if yes the date, percent inspired oxygen and percent oxygen saturation.

10.12 Bronchoscopy

A bronchoscopy with biopsy and/or bronchoalveolar lavage (BAL) will be performed only when medically necessary for ensuring patient care. When non-infectious pneumonitis is diagnosed, consultation with a pulmonologist should be considered.

A listing showing the assessment date, was infectious agent identified? (yes, no), was BAL done? (yes, no), was BAL cell count done? (yes, no), was alveolar hemorrhage seen? (yes, no) and if yes, the predominance (lymphocyte, eosinophil, neutrophil, dysplastic type II, malignant, other), was a transbronchial biopsy done? (yes, no) and if yes, the findings.

10.13 Chest X-ray or chest CT-scan

If the baseline scan shows signs suggestive of interstitial lung disease (ILD)/non-infectious pneumonitis, it is at the discretion of the investigator to follow the patient with appropriate chest imaging. For all other patients chest X-rays or chest CT-scans are to be performed during the study if clinically indicated e.g. if there is suspicion of non-infectious pneumonitis, in the investigator's discretion. A shift table displaying the baseline result (normal, insignificant abnormality, clinically significant abnormality) compared with the worst post-baseline categorized result will be produced. Percentages will be calculated using the number of patients with that categorized result at baseline as the denominator.

A listing split by treatment will be provided showing the X-ray/CT-scan date, the examination of the chest in the P-A and/or lateral view (normal, clinically insignificant abnormality, clinically significant abnormality) and if clinically significant, details of the abnormality.

10.14 Hepatic assessment

If certain criteria occur then one of the tests that must be carried out within **72 hours** of awareness of the abnormality is a hepatitis screen. This consists of anti-HAV (positive, negative, not done), IgM (positive, negative, not done) to confirm acute Hepatitis A, HbsAg (positive, negative, not done), Anti-HBc (positive, negative, not done), anti-HCV (positive, negative, not done) and if positive, PCR viral load, Anti-HEV ANA antibodies (positive, negative, not done), anti-smooth muscle anti-bodies (positive, negative, not done), CMV (positive, negative, not done) and EBV (positive, negative, not done). All these will be listed split by treatment arm along with the sample date, laboratory number and laboratory name.

10.15 Vital signs

Vital signs data includes weight, body temperature, respiratory rate, sitting pulse as well as sitting blood pressure (systolic and diastolic). Shift tables using the low/normal/high/(low and high) classification (as shown below.) will be produced to compare baseline to the worst on-treatment value with each vital sign parameter on a new page. Percentages will be calculated using the number of available patients at baseline with corresponding level and at least one non-missing post baseline value as the denominator. For baseline value classification (low/normal/high) the normal ranges per parameter will be taken into account (except for weight displaying only Total and Missing rows as there is no normal range defined). For post-baseline classification change from baseline will also be considered (except for respiratory rate). Only assessments obtained after start of study drug and up to 56 days after the discontinuation of study medication will be considered “on-treatment”.

Table 11 - Notable abnormalities

Vital signs	Notable abnormalities	
	Low	High
Pulse (beats/min)	$\leq 50 + \text{decrease} \geq 15^*$	$\geq 120 + \text{increase} \geq 15^*$
Blood pressure (mmHg)	Systolic $\leq 90 + \text{decrease} \geq 20^*$	$\geq 180 + \text{increase} \geq 20^*$
	Diastolic $\leq 50 + \text{decrease} \geq 15^*$	$\geq 105 + \text{increase} \geq 15^*$
Weight (kg)	decrease of $> 10\%$ during the study*	increase of $> 10\%$ during the study*
Respiratory rate (per min)	≤ 12	≥ 25

* Refers to post-baseline value as compared to baseline value

The notable abnormality of ‘ $\geq 120 + \text{increase} \geq 15$ ’ is interpreted as that the value at that visit is ≥ 120 and the increase from baseline is ≥ 15 .

The vital signs variables of weight, body temperature, respiratory rate, sitting pulse and sitting blood pressure (systolic and diastolic) will also be listed and clinically notable values/changes from baseline will be flagged. A separate listing containing all records for patients with clinically notable abnormal vital signs will also be generated.

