7.1.4.1 Criteria for premature patient withdrawal

Patients **may** voluntarily withdraw from the study or be dropped from it at the discretion of the investigator at any time. Patients may be withdrawn from the study if any of the following occur:

1. Disease progression
2. Unacceptable toxicity / adverse events which are not listed below
3. Clinically significant abnormal lab values
4. Clinically significant abnormal test procedure results
5. Protocol violation
6. Administrative problems
7. Pregnancy
8. Patient withdrawing informed consent
9. New anticancer therapy
10. Patient lost to follow-up
11. Death

In addition to the general withdrawal criteria, the following **study specific criteria** will also require study treatment discontinuation:

1. Patients experiencing unacceptable toxicity as described in [Table 6-1](#), [Table 6-2](#), [Table 6-4](#), [Table 6-5](#), [Table 6-6](#) and [Table 6-7](#).
2. Patient with blood glucose values consistently in excess of 250 mg/dL persisting after interruption of study drug in spite of continuous, appropriate therapeutic intervention(s).
3. Confirmed QTcF >470 msec and discontinuation recommended by a cardiologist after examination of cardiovascular risk factors.
4. Mean QTcF >500 msec measured by triplicate ECGs, and discontinuation recommended by a cardiologist, after ECG re-evaluation and confirmation of a mean QTcF value >500 msec.
5. Significant arrhythmia findings from Holter monitoring such as:
 - Any ventricular or supra-ventricular tachyarrhythmia associated with symptoms of hemodynamic compromise
 - Sustained ventricular tachycardia (>30 sec) irrespective of symptoms
 - Recurrent non-sustained VT (≥ 3 beats) during any 24-hour monitoring period
 - Torsades de Pointes (TdP)
 - Cardiac arrest
 - Pause >5 seconds
 - Second or third degree AV block.
6. New occurrence of clinically significant/symptomatic bradycardia.
7. Increased risk of QT prolongation by use of QT prolonging medication.
8. Hypokalemia (<3.5 mmol/L) or hypomagnesaemia (<0.7 mmol/L or below the LNR as provided by the laboratory) confirmed by repeat testing that is either a new finding or accompanied by vomiting or diarrhea and not corrected by treatment.

9. Abnormal Liver Function Tests such as:

- ALT or AST > 3 x ULN and Total Bilirubin \geq 2 x ULN and ALP < 2 x ULN;
- ALT or AST > 5 x ULN and \leq 8 x ULN persistent for more than 2 weeks;
- ALT or AST > 8 x ULN.

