- To assess the biochemical response rate (BRR), duration of biochemical response (DBR) and biochemical progression-free survival (BPFS) of pasireotide LAR and everolimus alone or in combination in patients with a well differentiated neuroendocrine tumor of the lung or thymus. The endpoint **“biochemical response rate (BRR)”** is the percentage of patients showing normalization, i.e. return to within normal ranges, or a decrease of $\geq 30\%$ from baseline of serum Chromogranin A (CgA) concentrations compared to baseline. The endpoint of **“duration of biochemical response (DBR)”** is defined as the time from the first documentation of biochemical response to the first documentation of biochemical progression (defined as an increase of serum CgA levels $\geq 25\%$ versus baseline) or to death due to any cause, whichever occurs first. The endpoint of **“biochemical progression free survival (BPFS)”** is the time from the first study drug administration to the first documentation of biochemical progression or to death due to any cause, whichever occurs first. Biochemical progression is defined as an increase of serum CgA levels $\geq 25\%$ versus baseline. Additionally, the biochemical response on the basis of urine 5-hydroxyindole acetic acid (5HIAA) will be assessed.
- To assess the safety and tolerability of pasireotide LAR and everolimus alone or in combination as measured by rate and severity of adverse events in patients with a well differentiated neuroendocrine tumor of the lung or thymus. Safety will be assessed using the Common Terminology Criteria for Adverse Events (CTCAE), version 4.0. Incidence of adverse events (AEs), serious adverse events (SAEs), changes from baseline in vital signs, ECG tracings and laboratory results (hematology, blood chemistry) will be reported.

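### The pulse and blood-pressure shift tables in SAP 10.15 classify baseline and on-treatment values by different rules, so a patient who stays abnormal can be tabulated as normal

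*SAP*

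**What the plan says.** SAP 10.15 defines the output: "Shift tables using the low/normal/high/(low and high) classification (as shown below.) will be produced to compare baseline to the worst on-treatment value". Percentages are taken within each baseline level, among patients with at least one post-baseline value.

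The two axes are then given separate rules. At baseline: "For baseline value classification (low/normal/high) the normal ranges per parameter will be taken into account". Weight is excepted because it has no normal range. After baseline: "For post-baseline classification change from baseline will also be considered (except for respiratory rate".

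Table 11 supplies the post-baseline criteria, each an absolute limit joined to a change for pulse and for systolic and diastolic pressure. Its footnote to the change component reads: "Refers to post-baseline value as compared to baseline value". The text under the table settles how the two parts combine. For high pulse, the criterion "is interpreted as that the value at that visit is" at least 120 "and the increase from baseline is" at least 15. Both conditions must therefore hold.

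The remaining outputs in 10.15 are listings: one of all vital signs with notable values flagged, and one of all records for patients with notable abnormal values.

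SAP 3.2 includes vital signs in the safety objective: "changes from baseline in vital signs, ECG tracings and laboratory results (hematology, blood chemistry) will be reported". Protocol 10.5.3.1.4 asks for descriptive analysis and listing, and leaves the definition of notable values to the SAP.

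**The concern.** A shift table is read along its rows: of those high at baseline, how many were high, normal or low at their worst on treatment. That reading needs the same scale at both times. Here a patient already beyond the limit must move a further 15 or 20 units in the same direction to keep the label held at baseline. No class is provided for a value beyond the limit that lacks the required change, so such a value can only go to normal.

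The abnormal baseline rows would then show apparent normalisation that includes patients who did not change or got worse. This is the only summary table of vital signs in 10.15, and SAP section 10 has all safety analyses rerun on cumulative data after the extension phase, so the same output would be produced twice.

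**Working it through.** The plan states no figure to reproduce. The check applies the two written rules to example patients.

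**Inputs (SAP 10.15, Table 11)**

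| Parameter | Low: limit and fall | High: limit and rise |
|---|---|---|
| Pulse (beats/min) | ≤50 and ≥15 | ≥120 and ≥15 |
| Systolic (mmHg) | ≤90 and ≥20 | ≥180 and ≥20 |
| Diastolic (mmHg) | ≤50 and ≥15 | ≥105 and ≥15 |

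**Assumption.** The SAP gives no numerical normal ranges for baseline. Table 11's absolute limits are used in their place.

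**Rule.** Let b be the baseline value, v the worst on-treatment value, H the high limit and d the required rise.

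- Baseline is high if b ≥ H.
- On treatment is high if v ≥ H and v − b ≥ d.
- If b ≥ H, the second condition implies the first, so the patient stays high only if v ≥ b + d.
- Any v from H up to just below b + d is beyond the limit but is not classed high. The low side mirrors this: the patient stays low only if v ≤ b − d.

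**Examples**

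| Parameter | b to v | Change against requirement | Rule as written | Limits only at both times |
|---|---|---|---|---|
| Systolic | 185 to 185 | 0 < 20 | high to normal | high to high |
| Systolic | 185 to 200 | 15 < 20 | high to normal | high to high |
| Systolic | 185 to 205 | 20 = 20 | high to high | high to high |
| Diastolic | 108 to 120 | 12 < 15 | high to normal | high to high |
| Pulse | 122 to 136 | 14 < 15 | high to normal | high to high |
| Pulse | 48 to 34 | 14 < 15 | low to normal | low to low |
| Pulse | 48 to 33 | 15 = 15 | low to low | low to low |

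For the patient starting at systolic 185, every worst value from 180 to 204 is tabulated as normal, since 185 + 20 = 205.

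**Patients exactly at a limit at baseline.** To keep their class they must reach:

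- systolic 180 + 20 = 200 or more, or 90 − 20 = 70 or less;
- diastolic 105 + 15 = 120 or more, or 50 − 15 = 35 or less;
- pulse 120 + 15 = 135 or more, or 50 − 15 = 35 or less.

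**Parameters not affected.** Respiratory rate uses limits only (≤12, ≥25). Weight has no baseline class, so no abnormal-to-normal shift can appear. Body temperature is named as a vital sign but has no row in Table 11, so it cannot be checked.

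**Comparison within the SAP.** In 10.8, QTcF is categorised at each visit, the baseline category is set against the worst post-baseline category, and patients with notable increases are counted separately. In 10.2, one grading or one low/normal/high classification serves both times. Section 10.15 departs from both.

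**The case against.** The strongest defence is that the combined criterion is deliberate and sensible. Requiring a change as well as a limit separates newly arising abnormality from abnormality present at entry. The SAP's document history records that the classification was clarified specifically for the shift table, and the protocol prescribes no vital-signs shift table. That justifies the criterion as a screen for new notable values. It does not justify using it on one axis only.

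It can also be said that the SAP nowhere states that such patients are tabulated as normal. That is correct: the result follows by elimination from the listed classes. The baseline figures are likewise assumed. Tighter normal ranges would put more patients in the abnormal baseline rows and enlarge the mismatch.

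Three stronger readings are tempting, but the documents do not support them.

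- **That persistent hypertension or bradycardia is hidden.** All values are listed. Protocol 7.2.2.2 sends vital signs that represent adverse events to the CRF, and SAP 10.1 tabulates events that start or worsen on treatment. What does stand is narrower: if notable means Table 11, the patient going from 185 to 200 is unflagged in the full listing, and these values would not bring that patient into the separate listing of notable cases.
- **That a stopping rule is weakened.** The criterion in Protocol 7.1.4.1 is "New occurrence of clinically significant/symptomatic bradycardia". It is applied to the individual patient during treatment, does not draw on this table, and concerns new occurrence rather than a low pulse carried over from baseline.
- **That all vital signs are affected.** Only pulse and the two blood pressures are. A patient with pulse 52 falling to 38, who stays normal throughout under these rules, shows how strict the combined criterion is. That patient is not an example of false normalisation.

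**Conclusion.** The point holds for pulse, systolic and diastolic pressure. As written, the rules place a patient who is beyond the limit at both times in the on-treatment normal class, unless the value has moved a further 15 beats/min, 20 mmHg systolic or 15 mmHg diastolic in the same direction.

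This rests on two things: reading the list of classes as complete, and, for the worked values, taking Table 11's limits as the baseline ranges. The documents give no baseline vital-sign data, so the number of patients affected cannot be stated. The consequence is a misleading descriptive safety table. The primary endpoint, the sample size and the error rates are untouched. It should still be corrected, because the stated rule produces a wrong shift and the remedy is small.

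**What to change.** In SAP 10.15:

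1. For pulse, systolic and diastolic pressure, state one numerical set of absolute limits and apply it to both the baseline and the worst on-treatment value in the shift table.
2. Add a frequency table of patients meeting the Table 11 limit-plus-change criterion, on the pattern of 10.8 for QTcF. The present listings flag these values but do not count them, so this table is new. Keep weight in it on its percent-change criterion.
3. Say how body temperature is to be classified, or that it is only listed.

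The cost is SAP wording, one re-programmed table and one small additional table. No new data are needed.

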10.16 Eastern Cooperative Oncology Group (ECOG) performance status (WHO)

The ECOG performance status is captured throughout the study. A shift table displaying the baseline category compared with the worst post-baseline category will be produced. Percentages will be calculated using the number of patients with that category at baseline as the denominator. A listing of all ECOG records will also be produced. In addition, bar charts will be created separately for each treatment group, displaying the percentage distribution of each ECOG performance score at each scheduled visit.

11 Interim analyses

An external and independent Data Monitoring Committee (DMC) was instituted before study start. The DMC will review safety-related issues and will be entitled to make recommendations for changes in study conduct, if needed during core phase of the study. Details on the function of the DMC are reported in a separate DMC Charter. A separate Module 3, Module 7.1 and Module 8.1 have been produced with details of what will be produced for each DMC.

12 Other topics

No other topics will be studied.

13 Determination of sample size

The trial tests the null hypothesis H_0 that the observed proportion of patients progression free, p , is less than or equal to p_0 against the alternative hypothesis H_1 that p is greater than or equal to p_1 . It consists of entering a predetermined number of patients and deciding in favor of p_0 or p_1 based on the success rate observed by using an appropriate cut-off between p_0 and p_1 . If the number of responses is greater than or equal to $R+1$, p_0 is rejected in favor of p_1 . If the number of responses less than or equal to R , p_1 is rejected in favor of p_0 .

For this study let p_0 be the highest proportion of patients progression-free at Month 9 which would indicate that the treatment is clearly ineffective, and p_1 be the minimum required proportion of patients progression-free for the procedure or treatment to be effective.

Table 12 – Design features for single arm trials

p_0	p_1	Target		Cut-Off $R + 1$	N	Actual	
		alpha	beta			alpha	beta
20%	45%	5%	10%	13	40	4.3%	4%

A study requires 40 patients per treatment to decide whether the proportion responding, p , is less than or equal to $p_0=20\%$ or greater than or equal to $p_1=45\%$. If the number of responses is 13 or more, the hypothesis that $p \leq p_0 = 20\%$ is rejected with a target alpha error rate of 5% and an actual alpha error rate of 4.3%. This indicates that the treatment is not ineffective i.e. it is likely be effective and so it is worth proceeding with a phase III trial. If the number of responses is 12 or less, the hypothesis that $p \geq p_1 = 45\%$ is rejected with a target beta error rate of 10% and an actual beta error rate of 4%. This indicates that the treatment is not effective i.e. is likely to be ineffective and so it is not worth pursuing any further.

14 References

Clopper CJ, Pearson ES (1934). The use of confidence or fiducial limits illustrated in the case of the binomial. *Biometrika*; 26, 404-413.

Fleming T (1982). One-sample multiple testing procedure for phase II clinical trials, *Biometrics* 38, 143-151.

